6. STUDY ASSESSMENT

6.1 Screening and enrolment

All patients who meet the basic enrolment criteria (fever or history of fever within the last 48 hours, symptoms of malaria, absence of danger signs in children in relation to malaria—child unable to drink or breastfeed, vomiting everything, recent history of convulsions, lethargic or unconscious state, unable to sit or stand, difficulty in breathing—, absence of signs of severe malaria, absence of severe malnutrition, pregnancy) during screening will be assigned a consecutive number and evaluated in greater depth by the health care staff at the study sites. In children, care will be taken to detect early signs of febrile diseases other than malaria, as their presence will necessitate exclusion from the evaluation. The most frequent confounding condition is a lower respiratory tract infection: cough or difficult breathing, together with fast breathing, is an indicator for exclusion. Fast breathing is defined as a respiratory frequency > 50/min in infants under 12 months of age and > 40/min in children aged 12–59 months. Other relatively common febrile conditions are otitis media, tonsillitis, measles and abscesses.

Patients with these conditions will not be enrolled but should be treated for both malaria (if they have parasitaemia) and the other infection, as appropriate.

The screening record form (Appendix 5) will be used to record the general information and the clinical observations on each patient being screened. If the patient meets the clinical criteria, he/she will be examined for presence of parasitaemia, initially with a RDT for malaria. For all screening patients with a positive RDT test, a confirmatory blood slide will be conducted to ensure presence of *P. falciparum* mono-infection. Once the patient meets all the enrolment criteria, he/she or a parent or guardian in case of children will be asked for consent to participate in the study.

6.2 Follow-up

Patients who meet all the enrolment criteria will be given a personal identification number and will receive treatment only after the study has been fully explained to them and they have willingly provided informed consent. Any person who decides not to participate in the study will be examined, treated and followed-up by the health facility staff according to the standard of care established by the Zanzibar Ministry of Health.

The basic follow-up schedule is summarized in Appendix 6. A case report form (Appendix 7) and a serious adverse event report form (Appendix 8) will be used to record the general information and clinical observations on each patient enrolled into the study. The appointment schedule will be clearly explained, and a follow-up card with a personal identification number will be provided.

The day a patient is enrolled and receives the first dose of study medicine is designated 'day 0'. All antimalarial treatment will be given by a study team member under supervision. Enrolled patients will be observed for at least 30 min after treatment to ensure that they do not vomit the medicine. If vomiting occurs within 30 min of treatment, the full treatment dose will be repeated. Ancillary treatment, such as antipyretics, will be provided if necessary to patients by the study team and documented on the case report form. Patients with persistent vomiting (i.e. necessitating more than a single repeat dose) will be excluded from the study and immediately referred to the health facility staff for appropriate management.

Thereafter, patients are required to undergo regular clinical reassessment. Blood films for asexual and gametocyte parasite counts will be made on days 2, 3 and 7 and then weekly for the remainder of the follow-up period, i.e. on days 14, 21 and 28. Patients will be advised to return on any day during the follow-up period if symptoms return and not to wait for the next scheduled visit day. In particular, parents or guardians should be instructed to bring children to the centre at any time if they show any sign of danger (unable to drink or breastfeed, vomiting everything, presenting with convulsions, lethargic or unconscious, unable to sit or stand, presenting with difficult breathing), if they are still sick or if there is any cause for worry. Clinical reassessment will be sufficiently thorough to ensure patient safety and will include assessment not only for potential treatment failure but also for potential adverse reactions to the medicine. Additionally, blood films will be obtained whenever parasitological reassessment is requested by the clinical staff.

Because many medicines have to be given over several days, the initial visits are critical not only for assessing efficacy but also for ensuring patient safety; defaulters at this stage will not have received a complete course of treatment and may be at risk for clinical deterioration. All reasonable efforts will be made to find defaulters to ensure complete treatment. Similarly, the ultimate success of the study rests on minimizing loss to follow-up. While patients are encouraged to return on their own for scheduled follow-up visits, it is essential that

provisions be made ahead of time for locating patients at home if they do not attend as requested. This requires obtaining detailed directions to the home during enrolment, and study team members familiar with the community will be responsible for home visits and means of transport for the patients. Health attendant (community mobiliser) of each facility will be involved in this study. His/her main responsibility will be to take detail record of each enrolled patient, if patient did not show up at health facility on his/her scheduled day then active follow up is done by community mobiliser. The schedule of treatment and follow-up examinations given in this protocol must be followed to ensure data integrity. Patients who fail to return on days 1 and 2 and miss one dose of the treatment will be withdrawn from the study definitively. After day 3, patients who fail to return on day 7 but are present on day 6 or 8 (likewise days 13/15, days 20/22, days 27/29 may still be included in the analysis. Deviation from the protocol of more than 1 day should, however, be avoided (see also section 3.7).

7. DATA MANAGEMENT

The principal investigator will ensure that the study protocol is strictly adhered to and that all data are collected and recorded correctly on the case report form. Laboratory and clinical data will be recorded on a daily basis on the case report form designed for the study. Data derived from source documents should be consistent with the source documents, or the discrepancies should be explained. Any change or correction to a case report form should be dated and explained and should not obscure the original entry. All case report forms will be checked for completeness.

After the study has been completed, data will be entered into a database by double independent data entry, according to WHO standard procedures (WHO/GMP). The trial data will be stored in a computer database, maintaining confidentiality.

The principal investigator is responsible for keeping all screening forms, the case report form and the completed subject identification code list in a secure location.

8. STATISTICAL METHODS

8.1 Sample size

Sample size calculations is based on an assumed PCR corrected treatment failure rate of artesunate and amodiaquine by day 28 of 5%, a confidence level of 95% and a precision of 5%. This corresponds to a sample of 73 + 20% to account for attrition, in total 90 patients.

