3. METHODS

3.1 Study design and clinical trial registration

This surveillance study is designed as a one-arm prospective evaluation of the clinical and parasitological responses to directly observed treatment for uncomplicated malaria WHO, 2003 and 2009). People with uncomplicated malaria, who meet the study inclusion criteria will be enrolled, treated on site with artesunate + amodiaquine and a single low dose of primaquine (0.25 mg/kg) and monitored for 28 days. The follow-up will consist of a fixed schedule of check-up visits and corresponding clinical and laboratory examinations. On the basis of the results of these assessments, the patients will be classified as having therapeutic failure (early or late) or an adequate response. Blood samples from patients experiencing therapeutic failure during the follow-up period will be used to estimate the efficacy of the study drugs based on PCR analysis to distinguish between recrudescence (treatment failures) and reinfection (new infections).

This study will be registered at the ClinicalTrials.gov registry platform before commencement of the trial.

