8.2 Analysis of data

Microsoft Excel-2007 program World Health Organization 2008 will be used for data management and analysis. Data will be double entered, validated and analysed by two methods: the Kaplan-Meier method and per-protocol analysis in accordance with WHO recommendations. In addition to the reasons for withdrawal listed in section 3.8, patients will be considered withdrawn from the analysis if the PCR results are unclassifiable or if the results of PCR indicate that the failure is due to reinfection with *P. falciparum* or *P. vivax*.

The final analysis and report will include:

- a description of all patients screened and the distribution of reasons for non-inclusion in the study;
- a description of all the patients included in the study;
- the proportion of adverse events and serious adverse events in all the patients included in the study;
- the proportion of patients lost to follow-up or withdrawn, with 95% confidence intervals and a list of reasons for withdrawal;
- the cumulative incidence of success and failure rates at day 28, PCR-uncorrected and PCR-corrected; and
- the proportion of early treatment failure, late clinical failure, late parasitological failure and adequate clinical and parasitological response at day 28, with 95% confidence intervals, PCR-uncorrected and PCR-corrected, as well as gametocyte carriage at each sampling occasion.
- polymorphism of genetic markers related to artesunate + amodiaquine tolerance/resistance.

Guidelines on calculating the cumulative success or failure rate, the proportion of adequate clinical and parasitological response and treatment failure are given in Appendix 9.

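### Section 8.1 computes 73 correctly, but from a normal approximation that fails at 3 to 4 expected failures, so 95% confidence with symmetric 5-point precision is not delivered

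*Combined protocol and SAP*

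**What the plan says.** Section 8.1 (Sample size) is the plan's only sample-size statement. It starts from a PCR-corrected "failure rate of artesunate and amodiaquine by day 28 of 5%, a confidence level of 95% and a precision of 5" per cent. It concludes: "This corresponds to a sample of 73 + 20% to account for attrition, in total 90 patients". It names no formula.

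Section 8.2 (Analysis of data) promises the day-28 outcome proportions, including "adequate clinical and parasitological response at day 28, with 95% confidence intervals, PCR-uncorrected and PCR-corrected". Neither 8.2 nor Appendix 9 (Guidelines for analysis of results) says whether those intervals are simple normal (Wald), Wilson or exact.

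Section 3.1 describes the study as "designed as a one-arm prospective evaluation of the clinical and parasitological responses". There is therefore no power, margin or comparison to set beside the precision statement.

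**The concern.** A precision-based sample size is only as good as the interval that it assumes. The simple formula takes the observed proportion to be roughly normal and symmetric about the true rate. With a rare outcome and a small sample, the count of failures is discrete and skewed to the right. The symmetric interval is then too short on the upper side and too often lies wholly below the true rate.

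Two things are at stake. First, 8.1 states a design property that the design does not have, and the error is in the upper limit for treatment failure, which is the limit of interest in an efficacy study. Second, because 8.2 leaves the method open, the simple interval could also be used for reporting. With no failures among those evaluable it would collapse to 0% to 0%.

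**Working it through.** **Inputs, all from 8.1:** failure rate p = 0.05; confidence 95%, taken as two-sided (z = 1.96); precision d = 0.05, read as the absolute half-width of the confidence interval; 73 evaluable; 20% attrition; 90 in total.

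**1. Reproduce the plan's figure.** n = z²p(1 − p)/d² = 1.96² × 0.05 × 0.95 / 0.05² = 72.99, rounded up to 73. This matches exactly.

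**2. Attrition.** 73 × 1.2 = 87.6 and 73/0.8 = 91.25; the stated 90 lies between them. Losing 20% of 90 leaves 90 × 0.8 = 72, one below 73.

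**3. Coverage of the simple interval.** The expected count is 73 × 0.05 = 3.65 failures. The interval is p̂ ± 1.96√(p̂(1 − p̂)/73), where p̂ is the observed proportion. At an observed 5% it is 0.0% to 10.0%, but an actual trial gives a whole number of failures:

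| Failures of 73 | Simple 95% interval | Contains 5%? |
|---|---|---|
| 0 | 0% to 0% | no |
| 1 | −1.3% to 4.0% | no |
| 2 | −1.0% to 6.5% | yes |
| 3 | −0.4% to 8.7% | yes |
| 4 | 0.3% to 10.7% | yes |
| 10 | 5.8% to 21.6% | no |

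Under a binomial with n = 73 and p = 0.05, P(0 or 1 failures) = 0.1145 and P(10 or more) = 0.0034. Coverage is 1 − 0.1145 − 0.0034 = 0.882. The lower limit is at or below zero whenever 3 or fewer failures are seen, which has probability 0.50.

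**4. Is 88% a freak value?** Coverage is saw-toothed in the true rate. With 73 evaluable:

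| True rate | Coverage of simple interval |
|---|---|
| 4% | 94.7% |
| 4.5% | 84.1% |
| 5% | 88.2% |
| 5.5% | 90.9% |
| 6% | 93.4% |

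On a fine grid from 3% to 7% the mean is 89.5% and the range is 79.7% to 94.8%. At a true 5% it is 87.8% with 72 evaluable and 93.8% with all 90.

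**5. Intervals that hold about 95%.** At n = 73 and a true 5%:

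| Method | Coverage | Mean half-width | Mean upper arm | Interval at 4/73 |
|---|---|---|---|---|
| Wilson | 94.7% | 5.2 points | 7.5 points | 2.2% to 13.3% |
| Exact (Clopper-Pearson) | 96.6% | 5.6 points | 7.6 points | 1.5% to 13.4% |

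**6. What 72 evaluable would give.** Wilson centre = (p̂ + z²/2n)/(1 + z²/n); half-width = z√(p̂(1 − p̂)/n + z²/4n²)/(1 + z²/n). For 4/72, p̂ = 0.0556, the centre is 0.0781 and the half-width 0.0563, so the interval is 2.2% to 13.4%. For 3/72 (4.2%) it is 1.4% to 11.5%.

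**The case against.** The strongest reply is that nothing was miscalculated: 73 is what a conventional planning formula gives. That stands. A reader might infer an arithmetic error, and there is none; the fault is in applying the approximation at this event count.

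Second, the plan does not commit to reporting the simple interval. If the analysis program produces Wilson or exact limits, the 88% never attaches to a published result. That also stands, so the 88% describes the planning claim and not the trial's eventual report. It does not rescue 8.1, because Wilson and exact intervals are not ±5 points either.

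Third, 8.1 does not define precision. If it meant only that the estimate falls within 5 points of the true rate, 73 patients achieve that with probability 97.1%. But 8.1 pairs precision with a confidence level and 8.2 reports confidence intervals, so the interval reading is the natural one. On half-width alone the shortfall is small (5.2 to 5.6 points against 5); the larger discrepancy is in the upper arm.

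Three further inferences should be resisted:

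- *Attrition was materially mishandled.* The gap is one patient, 72 against 73.
- *PCR exclusions cut the sample well below 72.* Section 8.2 says "patients will be considered withdrawn from the analysis if the PCR results are unclassifiable", and it treats reinfections likewise, but 8.1 does not say that its 20% leaves these out. Under Appendix 9, reinfections and other-species infections are censored, not removed, in the Kaplan-Meier analysis.
- *The Ministry will take 8.1 as a promise of an upper limit of 10%.* The documents contain no such statement and set no 10% decision threshold.

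**Conclusion.** The point holds as an invalid approximation in the planning statement. With 73 evaluable and a true failure rate of 5%, the interval that justifies 73 covers about 88%. Intervals that hold about 95% have an upper arm near 7.5 points, although their total width is only modestly above plan. This rests on precision meaning the half-width of a two-sided 95% confidence interval, on a binomial count, and on about 72 or 73 evaluable patients; with all 90 evaluable the coverage shortfall is about one point.

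It is worth correcting because 8.1 is the plan's only precision statement and 8.2 leaves the method open. It does not show that the trial is too small for its purpose: the documents set no target for the upper limit that 90 patients would miss.

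**What to change.** Keep 90 enrolled.

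- **Section 8.1:** replace the claim of 5% precision at 95% confidence with wording such as: *90 enrolled less 20% gives about 72 evaluable; with 3 or 4 failures (4.2% or 5.6%) the 95% Wilson interval is 1.4% to 11.5% or 2.2% to 13.4%.*
- **Section 8.2:** specify the Wilson method for the 95% intervals of the day-28 proportions, PCR-uncorrected and PCR-corrected, so that the report matches the plan and an outcome with no events still has a usable upper limit.

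The cost is one sentence in each section and no extra patients. The stated precision becomes slightly less favourable.

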Co-investigator	[name] Malaria Elimination Programme E-mail : [contact] [name] Zanzibar Malaria Elimination Programme E-mail : [contact]
Co-investigator	[name], MD, PhD, DTM&H, Karolinska Instituttet, stockholm, Sweden. E-mail: [contact] [name] [name], MD, PhD, DTM&H, Uppsala University, Uppsala, Sweden. E-mail: [contact]
Participating institutions	Mnazi mmoja hospital Zanzibar Malaria Elimination Programme Karolinska Institutet, Stockholm, Sweden Uppsala University, Uppsala, Sweden
Study dates	April to October 2017
Sponsors	Ministry of Health, Zanzibar, Tanzania [name]. Global Fund: QNB-M-MOH Karolinska Institutet and Uppsala University, Sweden
Clinical trial registration	The study will be registered at ClinicalTrials.gov prior to commencement of the trial

SUMMARY

Title: Efficacy and safety of artesunate + amodiaquine combined with a single low dose of primaquine (0.25 mg/kg) for the treatment of uncomplicated *Plasmodium falciparum* malaria in Zanzibar.

Background: Zanzibar introduced artemisinin combination therapy (ACT) for the treatment of uncomplicated *P. falciparum* malaria in 2003 with artesunate + amodiaquine as first-line treatment. Following wide scale deployment of ACT together with strengthened vector control with long lasting insecticidal nets (LLIN) and indoor residual spraying (IRS) the burden of malaria has declined markedly in Zanzibar to a level equivalent with malaria pre-elimination. Artesunate+amodiaquine has previously shown to be safe and highly efficacious with polymerase chain reaction (PCR) corrected cure rates >90% by day 42 in clinical trials conducted 2003/4 and 2005. Recently, and in line with WHO recommendations for low transmission settings, a single low dose of primaquine (0.25 mg/kg), a *P. falciparum* gametocytocidal drug, has been introduced as policy. However, no updated efficacy data of the firstline treatment for uncomplicated malaria are available from Zanzibar.

Objective: To assess the efficacy and safety of artesunate+amodiaquine combined with a single low dose of primaquine (0.25 mg/kg) for the treatment of uncomplicated *P. falciparum* malaria in Zanzibar.

Methods: A one-arm prospective antimalarial drug efficacy trial will be conducted.

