Artesunate + amodiaquine as well as artemether-lumefantrine have previously shown to be safe and highly efficacious, with polymerase chain reaction (PCR) corrected cure rates >90% by day 42 in clinical trials conducted 2003/4 ([name] et al 2005) and 2005 (Holmgren et al 2007) for the treatment of children with uncomplicated *P. falciparum* malaria in Zanzibar. Zanzibar has recently, and in line with WHO recommendations for low transmission settings, introduced as policy for uncomplicated malaria a single low dose of primaquine (0.25 mg/kg), a *P. falciparum* gametocytocidal drug, in addition to standard ATC. However, no recent efficacy data of the presently recommended first-line treatment are available.

The aim of this study is therefore to provide policymakers with updated efficacy and safety data of artesunate + amodiaquine in combination with a single low dose of primaquine (0.25 mg/kg) and data on genetic markers of ACT tolerance/resistance, proposed as an early warning system for development and spread of antimalarial drug resistance, in Zanzibar. The study protocol is based on the new WHO guidelines for surveillance of antimalarial drug efficacy (WHO 2014).

OBJECTIVES

The general objective of this study is to assess the therapeutic efficacy and safety of artesunate + amodiaquine combined with a single low dose of primaquine (0.25 mg/kg) for the treatment of uncomplicated *P. falciparum* malaria patients in Zanzibar.

The specific objectives are:

- to determine the clinical and parasitological efficacy of artesunate + amodiaquine and primaquine in the treatment of uncomplicated *Plasmodium falciparum* infection;
- to differentiate recurrent infections during follow-up, i.e. recrudescence from new infections, by PCR analysis;
- to evaluate the incidence of adverse events, particularly with regards to potential

hematological adverse events of primaquine; and

- to determine the polymorphism of molecular markers associated with artesunate + amodiaquine tolerance/resistance.
- to formulate recommendations, which will enable the Zanzibar Ministry of Health to make informed decisions about whether the current national antimalarial treatment guidelines should be updated or not.
- To determine efficacy rate of the first line treatment compared to the first efficacy trial thirteen years ago.

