Appendix 9. GUIDELINES FOR ANALYSIS OF RESULTS

	PCR-uncorrected results		
End-point for day X (X = 28 or 42)	Cumulative success or failure rate (Kaplan-Meier analysis)	Proportion (per-protocol analysis)	
Adequate clinical and parasitological response on day X	Success	Success	
Early treatment failure	Failure	Failure	
Late clinical failure before day 7	Failure	Failure	
Late clinical failure or late parasitological failure on or after day 7	Failure	Failure	
Other species infection	Censored day of infection	Excluded from analysis	
Lost to follow-up	Censored last day of follow-up according to timetable	Excluded from analysis	
Withdrawal and protocol violation	Censored last day of follow-up according to timetable before withdrawal or protocol violation	Excluded from analysis	

End-point for day X	PCR-corrected results		
(X = 28 or 42)	Cumulative success or failure rate (Kaplan-Meier analysis)	Proportion (per-protocol analysis)	
Adequate clinical and parasitological response at day X	Success	Success	
Early treatment failure	Failure	Failure	
Late clinical failure before day 7	Failure	Failure	
Late clinical failure or late parasitological failure on or after day 7			
falciparum recrudescence*	Failure	Failure	
falciparum reinfection*	Censored day of reinfection	Excluded from analysis	
other species mixed with falciparum recrudescence	Failure	Failure	
other species mixed with falciparum reinfection	Censored day of reinfection	Excluded from analysis	
other species infection	Censored day of infection	Excluded from analysis	
 undetermined or missing PCR 	Excluded from analysis	Excluded from analysis	
Lost to follow-up	Censored last day of follow-up according to timetable	Excluded from analysis	
Withdrawal and protocol violation	Censored last day of follow-up according to timetable before protocol violation or withdrawal	Excluded from analysis	

^{*} WHO. Methods and techniques for clinical trials on antimalarial drug efficacy: genotyping to identify parasite populations. Geneva, World Health Organization, 2008 (http://www.who.int/malaria/resistance).

REFERENCES

- Bhattarai A et al., Impact of artemisinin-based combination therapy and insecticide-treated nets on malaria burden in Zanzibar. PLoS Med, 2007. 4(11): p. e309.
- Dahlström S et al., Diversity of the sarco/endoplasmic reticulum Ca₂+-ATPase orthologue of Plasmodium falciparum (PfATP6). Infect Genet Evol. 2008 May; 8 (3):340-5. Epub 2008 Feb 15

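### Is a sample sized only for 5-point precision too small for the stated comparison with the first efficacy trial?

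*Combined protocol and SAP*

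**What the plan says.** Section 8.1 takes a PCR-corrected failure rate of 5% by day 28, with "a confidence level of 95% and a precision of 5" percentage points. It concludes: "This corresponds to a sample of 73 + 20% to account for attrition, in total 90 patients". It gives no power, null value, margin or comparator.

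The Objectives include "To determine efficacy rate of the first line treatment compared to the first efficacy trial thirteen years ago". They also ask for recommendations that let the Ministry "make informed decisions about whether the current national antimalarial treatment guidelines should be updated or not".

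The only earlier efficacy result in the document is in the Summary, repeated in the Background: "corrected cure rates >90% by day 42 in clinical trials conducted 2003/4 and 2005".

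Section 8.2 promises "the cumulative incidence of success and failure rates at day 28, PCR-uncorrected and PCR-corrected", with no mention of an interval. For the outcome proportions at day 28 it promises estimates "with 95% confidence intervals, PCR-uncorrected and PCR-corrected". Appendix 9 ("GUIDELINES FOR ANALYSIS OF RESULTS") sets out which outcomes count as success, failure, censored or excluded. Neither place names an interval formula or an efficacy analysis against the earlier trial. The only historical method named is the trend analysis in section 5.2.5, and it concerns the genetic markers.

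**The concern.** One objective is a comparison with an earlier trial, and another is advice on national treatment policy. The sample size addresses neither. If the policy question is read as whether cure is still above 90%, then at the plan's own 5% failure rate the interval will usually include 90%. The Ministry would have no agreed way to read that result.

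The unnamed interval method adds to the worry. With 3 failures in 73, the lower limit for cure is 91.3% by Wald, 88.6% by Wilson and 88.5% by Clopper-Pearson. The choice of method would decide on which side of 90% the limit falls, and it could be made after the data are seen.

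**Working it through.** **Inputs.** From section 8.1: failure rate p = 0.05, half-width d = 0.05, 95% confidence, 73 evaluable, 20% attrition, 90 enrolled. Assumption, not in the plan: a threshold of 90% cure (10% failure).

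**1. The plan's own figure.** n = 1.96² × p(1 − p)/d² = 3.8416 × 0.0475/0.0025 = 72.99, so 73. For attrition, 73 × 1.2 = 87.6 and 73/0.8 = 91.25; the stated 90 lies between them. The figure reproduces.

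**2. Is the precision delivered?** Weighting the interval limits by Binomial(73, 0.05), the expected Wilson interval for failure is 2.0% to 12.5%, a half-width of about 5.2 points. Clopper-Pearson gives 5.6 and Jeffreys 4.9. With 90 evaluable the expected Wilson interval is 2.2% to 11.5%, a half-width of about 4.7 points. The interval is asymmetric, but its width is close to what was planned.

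**3. Chance that the upper limit for failure is below 10%, true failure 5%.**

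| Evaluable | Method | Most failures allowed | Upper limit there | Upper limit with one more | Chance |
|---|---|---|---|---|---|
| 73 | Wilson | 2 | 9.45% | 11.40% | 28.7% |
| 73 | Clopper-Pearson | 2 | 9.55% | 11.54% | 28.7% |
| 73 | Wald | 3 | 8.66% | 10.70% | 50.1% |
| 90 | Wilson | 3 | 9.35% | 10.88% | 33.6% |
| 90 | Clopper-Pearson | 3 | 9.43% | 10.99% | 33.6% |
| 90 | Wald | 4 | 8.70% | 10.29% | 53.0% |

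These are values at two sample sizes, not the ends of a range. Failures are whole numbers, so the chance moves in a saw-tooth. By Wilson it falls to 20.9% at n = 83, jumps to 39.0% at n = 84, and is 33.6% at n = 90. Having 90 evaluable would also require no attrition, against the 20% allowed.

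**4. Dependence on the assumed inputs.** Wilson interval, n = 73 and n = 90:

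- True failure 5%, threshold 92% cure: 11.5% and 16.6%.
- True failure 5%, threshold 88% cure: 50.1% and 53.0%.
- True failure 5%, threshold 85% cure: 69.9% and 83.6%.
- True failure 3%, threshold 90% cure: 62.5% and 71.5%.
- True failure 2%, threshold 90% cure: 82.0% and 89.3%.

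The result therefore runs from 11.5% to 89.3%, depending on two inputs that the plan does not tie together.

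**5. Would a threshold rule help?** Suppose the report had to say whether the Wilson interval for cure lies above, includes or lies below 90%. To lie below would take at least 13 failures in 73 (17.8%) or 15 in 90 (16.7%). At a true failure rate of 15% that happens in 30% of trials with 73 and 37% with 90. So true failure rates of 5% and 15% would both usually be reported as inconclusive.

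**6. Would more patients help?** An 80% chance of an interval above 90% at true cure 95% is first reached at 217 evaluable patients (Wilson) and holds for every n from 254. That is about three times 73 (217/73 = 3.0; 254/73 = 3.5), for a criterion the plan does not set.

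**The case for a change.** The strongest case for a change does not need the 90% line. A stated objective has no efficacy analysis in section 8.2 or Appendix 9, the intervals have no named method, and the Kaplan-Meier rates have no promised interval. A few sentences would close all three gaps without touching enrolment, and naming the method beforehand removes a choice that could be made after the data are seen.

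These three omissions are real. They do not make the plan wrong or leave its main estimate in doubt. The day-28 PCR-corrected proportions will be reported with 95% intervals. Setting that estimate beside the earlier trial's published result meets the objective as worded, and an analyst would take care over the difference in follow-up day. A standard interval accompanies Kaplan-Meier estimates as a matter of course. Section 8.2 also ties the analysis to a WHO program and WHO recommendations, which may settle the interval method, although the document does not say so.

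The argument about sample size is weaker. The earlier result is a lower bound, at day 42, for two trials together. In the Background it covers two drug combinations in children. This study ends at day 28, enrols from 3 months of age with no upper limit, and adds primaquine. A one-sample threshold of 90% is one possible reading of the comparison, and the plan does not adopt it. The contrast between methods at 3 failures in 73 matters chiefly against that line.

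**Conclusion.** No change to the plan follows. Section 8.1 is correct for its stated purpose: 73 evaluable patients give an interval of roughly 5 points either side of a 5% failure rate. It makes no claim about confirming cure above 90%, so there is nothing to disclaim. A fixed 90% rule would import a debatable threshold and would usually return an inconclusive result at both 5% and 15% true failure.

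The low chance of an interval above 90% (28.7% at 73 and 33.6% at 90 by Wilson or exact, about 50% and 53% by Wald) is correct arithmetic. It rests on true cure of exactly 95% and on 90% as the benchmark. It describes a question that the study was not sized to answer. The gaps in section 8.2 are minor missing detail that analysts fill sensibly: the earlier estimate alongside the new one, a score or exact interval for the proportions, and an interval for the Kaplan-Meier rates.
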